***Male Subjects***

- Counseling about the requirement for condom use during sexual contact with FCBP and the potential risks of fetal exposure must be conducted at a minimum of every 28 days.
- If pregnancy or a positive pregnancy test does occur in the partner of a male study subject during study participation, the investigator must be notified immediately.

**Additional precautions**

- Subjects should be instructed never to give this medicinal product to another person and to return any unused capsules to the investigator at the End-of-Treatment.
- Subjects should not donate blood during therapy and for at least 28 days following discontinuation of pomalidomide.
- Male subjects should not donate semen or sperm during therapy or for at least 90 days following discontinuation of pomalidomide.
- Only enough pomalidomide for 1 cycle of therapy may be dispensed with each cycle of therapy.

Approved

---

CONFIDENTIAL

**APPENDIX J POMALIDOMIDE EDUCATION AND COUNSELLING  
GUIDANCE DOCUMENT**

**Protocol Number: OPZ007**

Patient Name (Print): \_\_\_\_\_ DOB: \_\_\_\_ / \_\_\_\_ / \_\_\_\_ (mm/dd/yyyy)

**Female**

**If female, check one:**

FCBP (female of childbearing potential): Sexually mature female who: 1) has not undergone a hysterectomy (the surgical removal of the uterus) or bilateral oophorectomy (the surgical removal of both ovaries) or 2) has not been naturally postmenopausal (amenorrhea following cancer therapy does not rule out childbearing potential) for at least 24 consecutive months (i.e., has had menses at any time during the preceding 24 consecutive months)

NOT FCBP

**To be completed prior to each dispensing of pomalidomide**

**Do Not Dispense pomalidomide if:**

- The patient is pregnant.
- No pregnancy tests were conducted for a FCBP.
- The patient states she did not use TWO reliable methods of birth control (unless practicing complete abstinence of heterosexual intercourse) [at least 28 days prior while taking pomalidomide, during dose interruption, and 28 days after discontinuation of pomalidomide].

**FCBP**

**1. I verified that the required pregnancy tests performed are negative.**

**2. I counseled FCBP regarding the following:**

- Potential fetal harm: If pomalidomide is taken during pregnancy, it may cause birth defects or death to any unborn baby. Females are advised to avoid pregnancy while taking pomalidomide. The teratogenic potential of pomalidomide in humans cannot be ruled out. Females of childbearing potential must agree not to become pregnant while taking pomalidomide.

Approved

CONFIDENTIAL

- Using TWO reliable methods of birth control at the same time or complete abstinence from heterosexual intercourse [at least 28 days prior, while taking pomalidomide, during dose interruption, and 28 days after discontinuation of pomalidomide].
- Continuation of TWO reliable methods of birth control or complete abstinence if therapy is interrupted.
- That even if she has amenorrhea she must comply with advice on contraception.
- Use of one highly effective method and one additional method of birth control AT THE SAME TIME. The following are examples of highly effective and additional effective methods of contraception:
  - Highly effective methods:
    - Intrauterine device (IUD)
    - Hormonal (birth control pills, injections, implants)
    - Tubal ligation
    - Partner’s vasectomy
  - Additional effective methods:
    - Male condom
    - Diaphragm
    - Cervical cap
- Pregnancy tests before and during treatment, even if the patient agrees not to have reproductive heterosexual intercourse. Two pregnancy tests will be performed prior to receiving study drug, one within 10–14 days and the second within 24 hours of the start of pomalidomide.
- Frequency of pregnancy tests to be done:
  - Every week during the first 28 days of this study and a pregnancy test every 28 days during the patient’s participation in this study if menstrual cycles are regular or every 14 days if cycles are irregular.
  - If the patient missed a period or has unusual menstrual bleeding.
  - When the patient is discontinued from the study and at Day 28 after study drug discontinuation if menstrual cycles are regular. If menstrual cycles are irregular, pregnancy tests will be done at discontinuation from the study and at Days 14 and 28 after study drug discontinuation.
- Stop taking pomalidomide immediately in the event of becoming pregnant and to call their study doctor as soon as possible.
- NEVER share pomalidomide with anyone else.

Approved

- Do not donate blood while taking pomalidomide and for 28 days after stopping pomalidomide.
- Do not breastfeed a baby while participating in this study and for at least 28 days after study drug discontinuation.
- Do not break, chew, or open pomalidomide capsules.
- Return unused pomalidomide to the investigator.

**3. Provide Pomalidomide Information Sheet to the patient.**

**Female not of childbearing potential (natural menopause for at least 24 consecutive months, a hysterectomy, or bilateral oophorectomy):**

**1. I counseled the female NOT of childbearing potential regarding the following:**

- Potential fetal harm (Refer to item #2 in FCBP).
- NEVER share pomalidomide with anyone else.
- Do not donate blood while taking pomalidomide and for 28 days after stopping pomalidomide.
- Do not break, chew, or open pomalidomide capsules.
- Return used pomalidomide capsules to the investigator.

**2. Provide Pomalidomide Information Sheet to the patient.**

**Male**

**1. I counseled the Male patient regarding the following:**

- Potential fetal harm (Refer to item #2 in FCBP).
- To engage in complete abstinence or use a condom when engaging in sexual intercourse (including those who have had a vasectomy) with a FCBP, while taking pomalidomide, during dose interruptions, and for 28 days after stopping pomalidomide.
- Males should notify their study doctor when their female partner becomes pregnant and female partners of males taking pomalidomide should be advised to call their healthcare provider immediately if they get pregnant.
- NEVER share pomalidomide with anyone else.
- Do not donate blood while taking pomalidomide and for 28 days after stopping pomalidomide.
- Do not donate semen or sperm while taking pomalidomide and for 90 days after stopping pomalidomide.
- Do not break, chew, or open pomalidomide capsules.

Approved

Onyx Therapeutics  
Oprozomib ER Tablets

Clinical Study Protocol No. OPZ007  
Page 146 of 223

- Return unused pomalidomide capsules to the Investigator.
- 2. Provide Pomalidomide Information Sheet to the patient.**

Investigator/Counselor Name (Print): \_\_\_\_\_  
(circle applicable)

Investigator/Counselor Signature: \_\_\_\_\_ Date: \_\_\_\_/\_\_\_\_/\_\_\_\_  
(circle applicable)

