
Approved

Inclusion criteria (cont'd):	Ethical/Other 

13. Patient must sign a written informed consent form in accordance with federal, local, and institutional guidelines

14. Female patients of childbearing potential must have a negative pregnancy test (with a sensitivity of at least 50 mIU/mL) within 1 day of the first dose of study drug, and agree to use 2 effective methods of contraception during the study and for 28 days following the last dose of study drug. Postmenopausal females (> 45 years old and without menses for <math>\geq 2</math> years) and surgically sterilized females are exempt from these requirements.

15. Male patients, including those with prior vasectomy, must use an effective barrier method of contraception during the study and for 3 months following the last dose if sexually active with a female of childbearing potential. Additionally, they must agree not to donate sperm while being treated and for up to 3 months after discontinuing treatment.

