### Ethical/Other

14. Patient must sign a written informed consent form in accordance with federal, local, and institutional guidelines.
15. Female patients of childbearing potential must have a negative pregnancy test (with a sensitivity of at least 50 mIU/mL) within 1 day of the first dose of study drug and agree to use 2 effective methods of contraception during the study and for 28 days following the last dose of study drug. Postmenopausal females (> 45 years old and without menses for  $\geq 2$  years) and surgically sterilized females are exempt from these requirements.
16. Male patients, including those with prior vasectomy, must use an effective barrier method of contraception during the study and for 3 months following the last dose if sexually active with a female of childbearing potential. Additionally, they must agree not to donate sperm while being treated and for up to 3 months after discontinuing treatment.

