Male subjects must use an effective barrier method of contraception during the study and for 3 months following the last dose if sexually active with a female of childbearing potential.

Because pomalidomide is present in the semen of male subjects who receive it, they must always use a latex or synthetic condom during any sexual contact with females of reproductive potential and for up to 3 months after discontinuation of study treatment, even if they have undergone a successful vasectomy. Male subjects must agree not to donate sperm while being treated and for up to 3 months after discontinuing treatment.

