***Male Subjects***

Must practice complete abstinence or agree to use a condom during sexual contact with FCBP while participating in the study, during dose interruptions, and for at least 90 days following study drug discontinuation, even if he has undergone a successful vasectomy.

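### The Appendix J counselling form gives men 28 days of condom use after stopping pomalidomide; the rest of the protocol requires 3 months or at least 90 days

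*Protocol*

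**What the plan says.** The Appendix J male list asks the counsellor to advise abstinence or a condom with a female of childbearing potential while the man takes pomalidomide, "during dose interruptions, and for 28 days after stopping pomalidomide". Two other bullets in that list also set post-treatment periods: 28 days for blood donation, and for semen "Do not donate semen or sperm while taking pomalidomide and for 90 days after stopping pomalidomide".

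The same male precaution appears elsewhere in the protocol:

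- Synopsis, inclusion criterion 15: men "must use an effective barrier method of contraception during the study and for 3 months following the last dose".
- Section 6.1, criterion 16: the same rule, "for 3 months following the last dose if sexually active with a female of childbearing potential".
- Section 10.6.1.1: "Male subjects must use an effective barrier method of contraception during the study and for 3 months following the last dose". A second sentence there, on condoms, says "for up to 3 months after discontinuation of study treatment".
- Appendix I, male subjects before starting study drug: abstinence or a condom "while participating in the study, during dose interruptions, and for at least 90 days following study drug discontinuation".

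The SAP does not deal with contraception.

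**The concern.** The form contradicts the rule it is meant to convey. Section 10.6.1.1 explains why condoms are required: "Because pomalidomide is present in the semen of male subjects who receive it". Appendix I reports that pomalidomide was teratogenic in rabbits and is an analogue of thalidomide, a known human teratogen. A counsellor who follows the form exactly would tell a man that he can stop the precaution well before the protocol allows.

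The form is marked for completion before each dispensing, and Appendix I limits each dispensing to one cycle's supply. Appendix I also requires men to be counselled on condom use at least every 28 days. The short period would therefore be repeated throughout treatment. What is at stake is fetal exposure in partners of male subjects. No endpoint, analysis set or estimate depends on it.

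**Working it through.** This is a comparison of texts with one subtraction. The protocol gives no derivation of the 28 days to reproduce.

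**Periods after treatment for male condom use or abstinence**

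| Place | Period | Counted from |
|---|---|---|
| Synopsis, criterion 15 | 3 months | last dose |
| Section 6.1, criterion 16 | 3 months | last dose |
| Section 10.6.1.1, first sentence on men | 3 months | last dose |
| Section 10.6.1.1, condom sentence | up to 3 months | end of study treatment |
| Appendix I, male subjects | at least 90 days | end of study drug |
| Appendix J, male condom bullet | 28 days | stopping pomalidomide |

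The Synopsis and Section 6.1 state one eligibility criterion twice, so the longer period rests on three distinct statements: the criterion, Section 10.6.1.1 and Appendix I.

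**Could 28 days be intended for men?** The protocol's other 28-day post-treatment periods concern female contraception, pregnancy testing, breastfeeding and blood donation. The Appendix I heading that mentions 28 days after discontinuation introduces testing and counselling; it does not shorten the male condom period stated just before it. The form itself uses 90 days for semen donation, so 28 days is not its general convention for men.

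**Size**

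- Shortfall against Appendix I: 90 − 28 = 62 days.
- Share covered: 28 / 90 = 31%.
- Share missing: 62 / 90 = 69%.
- If 3 calendar months is taken as 89 to 92 days (an assumption about calendar length), the shortfall is 89 − 28 = 61 to 92 − 28 = 64 days.

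These figures compare durations as if every period began on the same day.

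**The case against.** **The binding rules are already right.** The eligibility criterion, Section 10.6.1.1 and Appendix I all set the longer period, and the form also has the counsellor hand over the Pomalidomide Information Sheet, which is not available for this review. This stands as a limit on what can be said about practice. It does not remove the conflict: the form is the text the counsellor works from and signs, and its instruction and the Appendix I rule cannot both be the complete instruction.

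**Section 10.6.1.1 says up to 3 months, which taken alone would not exclude 28 days.** That wording is loose. But the same section states a firm 3 months immediately before it, and Appendix I sets a minimum of 90 days.

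**The correction may have little practical value.** The protocol's opening statement says that Amendment 3 was approved but not implemented because the program was terminated. The Amendment 3 summary of changes lists no edit to this form, which hints that the wording may be older. That table covers significant changes only, and the Amendment 2 form is not available, so this is a reason to check and not evidence.

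**A reader might infer a second error in the starting point.** The bullet counts from stopping pomalidomide and Appendix I from stopping study drug. Section 5.1.3 defines study drug as the three-drug combination, and Section 10.1 lets a subject stop pomalidomide and stay on study. On that reading the gap could exceed 62 days. The documents do not settle it. The definition sits in the section on dose-limiting toxicity. Appendix I is about pomalidomide and uses the two terms loosely: its pre-treatment pregnancy testing moves between them, and its semen-donation period runs from stopping pomalidomide. Against that, Section 10.6.1.1 speaks of study treatment and the eligibility criterion of the last dose. The text is ambiguous, and any gap beyond about 62 days would need an assumed interval between stopping pomalidomide and stopping the other drugs.

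**Conclusion.** The duration in the Appendix J male condom bullet is wrong as written. It gives 28 days where the protocol elsewhere requires 3 months or at least 90 days: 31% of the required period, or about 62 days (69%) short. The comparison takes Appendix I's 90 days as the reference and a common starting day; reading 3 months by the calendar moves the shortfall only to between 61 and 64 days.

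It applies to men who are sexually active with a female of childbearing potential, and the documents do not say how many that would be. They also give no data on semen clearance or on risk between day 29 and day 90, so the size is a gap in the instruction and not an estimate of harm.

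A reader might go on to infer that men in the trial were misinformed. The documents do not support that: they show what the form says, not what was said to anyone.

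**What to change.** In the Appendix J male condom bullet, change the period after stopping pomalidomide from 28 days to at least 90 days. Leave the 28-day blood-donation bullet as it is, since it agrees with Appendix I. The cost is one clause in one form.

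Do not change the starting point in the same edit. If the sponsor wants the period to run from the end of all study drug, that is a separate decision and should be applied to the condom and semen-donation bullets together, so that the list does not end up with two clocks. The sponsor should also check whether the counselling form and Information Sheet used under Amendment 2 carry the same 28 days.

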**APPENDIX L ACTG BRIEF PERIPHERAL NEUROPATHY SCREENING TOOL**

Source: NIAID Adult AIDS Clinical Trials Group

**1. Elicit Subjective Symptoms**

Ask the patient to rate the severity of each symptom listed in Question 1 on a scale of 01 (mild) to 10 (most severe) for right and left feet and legs. Enter the score for each symptom in the columns marked R (right lower limb) and L (left lower limb). If a symptom has been present in the past, but not since the last visit, enter "00 - Currently Absent." If the symptom has never been present, enter "11 - Always Been Normal."

Always Been Normal	Currently Absent	Mild ↔ Severe											
		01	02	03	04	05	06	07	08	09	10		
11	00											R	L
Symptoms													
a. Pain, aching, or burning in feet, legs													
b. "Pins and needles" in feet, legs													
c. Numbness (lack of feeling) in feet, legs													

Approved

**2. Grade Subjective Symptoms**

Use the single highest severity score from Question 1 above to obtain a subjective sensory neuropathy score. If all severity scores are "00" or "11," the subjective sensory neuropathy score will equal "0."

**APPENDIX M ACTG BRIEF PERIPHERAL NEUROPATHY SCREENING TOOL  
(CONT'D)**

**Subjective Sensory Neuropathy Score** (based on highest severity rating)

01–03 = grade of 1

04–06 = grade of 2

07–10 = grade of 3

11 or 00 = grade of 0

R	L

**3. Evaluate Perception of Vibration**

Compress the ends of a 128-Hz tuning fork just hard enough that the sides touch. Place the vibrating tuning fork on a bony prominence on the patient's wrist or hand to be sure that he/she can recognize the vibration or "buzzing" quality of the tuning fork. Again, compress the ends of the tuning fork just hard enough that the sides touch. Immediately place the vibrating tuning fork gently but firmly on the top of the distal interphalangeal (DIP) joint of one great toe and begin counting the seconds. Instruct the patient to tell you when the "buzzing" stops. Repeat for the other great toe.

**Vibration perception**

- a. Great toe DIP joint perception of vibration in seconds
- b. Vibration perception score

0 = felt > 10 seconds (normal)

1 = felt 6–10 seconds (mild loss)

2 = felt < 5 seconds (moderate loss)

3 = not felt (severe loss)

8 = unable to or did not assess

R	L

Approved

**APPENDIX M ACTG BRIEF PERIPHERAL NEUROPATHY SCREENING TOOL  
(CONT'D)**

**4. Evaluate Deep Tendon Reflexes**

With the patient seated, the examiner uses one hand to press upward on the ball of the foot, dorsiflexing the patient's ankle to 90 degrees. Using a reflex hammer, the examiner then strikes the Achilles tendon. The tendon reflex is felt by the examiner's hand as a plantar flexion of the foot, appearing after a slight delay from the time the Achilles tendon is struck. Use reinforcement by having the patient clench his/her fist before classifying the reflex as absent.

**Ankle Reflexes Score**

- 0 = absent
- 1 = hypoactive
- 2 = normal deep tendon reflexes
- 3 = hyperactive
- 4 = clonus
- 8 = unable to or did not assess

R	L

From Peripheral Neuropathy  
**Primary Care of Veterans with HIV**  
Office of Clinical Public Health Programs  
Veterans Health Administration, 2009

Approved

**APPENDIX M SAMPLE BRIEF PAIN INVENTORY – SHORT FORM (BPI-SF)**

Source: [Cleeland 2006](#).

Date: \_\_\_\_\_ Study ID: \_\_\_\_\_

Hospital: \_\_\_\_\_

[figure not shown]
---

**Brief Pain Inventory (Short Form)**

1. Throughout our lives, most of us have had pain from time to time (such as minor headaches, sprains, and toothaches). Have you had pain other than these everyday kinds of pain today?

Yes  No

2. On the diagram, shade in the areas where you feel pain. Put an X on the area that hurts the most.

3. Please rate your pain by marking the box beside the number that best describes your pain at its **worst** in the last 24 hours.

0  1  2  3  4  5  6  7  8  9  10

No Pain Pain As Bad As You Can Imagine

4. Please rate your pain by marking the box beside the number that best describes your pain at its **least** in the last 24 hours.

0  1  2  3  4  5  6  7  8  9  10

No Pain Pain As Bad As You Can Imagine

5. Please rate your pain by marking the box beside the number that best describes your pain on the **average**.

0  1  2  3  4  5  6  7  8  9  10

No Pain Pain As Bad As You Can Imagine

6. Please rate your pain by marking the box beside the number that tells how much pain you have **right now**.

0  1  2  3  4  5  6  7  8  9  10

No Pain Pain As Bad As You Can Imagine

Page 1 of 2 Copyright 1991 [name]  
Pain Research Group  
All rights reserved

Approved

Date: \_\_\_\_\_ Study ID: \_\_\_\_\_

Hospital: \_\_\_\_\_

---

**7. What treatments or medications are you receiving for your pain?**

**8. In the last 24 hours, how much relief have pain treatments or medications provided? Please mark the box below the percentage that most shows how much relief you have received.**

0%   10%   20%   30%   40%   50%   60%   70%   80%   90%   100%

No Relief Complete Relief

**9. Mark the box beside the number that describes how, during the past 24 hours, pain has interfered with your:**

**A. General Activity**

0    1    2    3    4    5    6    7    8    9    10  
 Does Not Completely Interfere

**B. Mood**

0    1    2    3    4    5    6    7    8    9    10  
 Does Not Completely Interfere

**C. Walking ability**

0    1    2    3    4    5    6    7    8    9    10  
 Does Not Completely Interfere

**D. Normal Work (include both work outside the home and housework)**

0    1    2    3    4    5    6    7    8    9    10  
 Does Not Completely Interfere

**E. Relations with other people**

0    1    2    3    4    5    6    7    8    9    10  
 Does Not Completely Interfere

**F. Sleep**

0    1    2    3    4    5    6    7    8    9    10  
 Does Not Completely Interfere

**G. Enjoyment of life**

0    1    2    3    4    5    6    7    8    9    10  
 Does Not Completely Interfere

Page 2 of 2      Copyright 1991 [name]  
 Pain Research Group  
 All rights reserved

Approved

**APPENDIX N EXAMPLE ELECTRONIC SERIOUS ADVERSE EVENT  
 CONTINGENCY REPORT FORM**

AMGEN Study # 20130411 Oprozomib		Electronic Serious Adverse Event Contingency Report Form For Restricted Use						
Reason for reporting this event via fax The Clinical Trial Database (eg. Rave):  Is not available due to internet outage at my site  Is not yet available for this study  Has been closed for this study <<For completion by COM prior to providing to sites: SELECT OR TYPE IN A FAX!>>								
1. SITE INFORMATION								
Site Number		Investigator			Country			
Reporter		Phone Number ( )		Fax Number ( )				
2. SUBJECT INFORMATION								
Subject ID Number		Age at event onset		Sex  F  M	Race	If applicable, provide End of Study date		
If this is a follow-up to an event reported in the EDC system (eg, Rave), provide the adverse event term: _____ and start date: Day ____ Month ____ Year ____								
3. SERIOUS ADVERSE EVENT								
Provide the date the Investigator became aware of this information: Day ____ Month ____ Year ____								
Serious Adverse Event diagnosis or syndrome If diagnosis is unknown, enter signs / symptoms and provide diagnosis, when known, in a follow-up report List one event per line. If event is fatal, enter the cause of death. Entry of "death" is not acceptable, as this is an outcome.	Date Started	Date Ended	Check only if event occurred before first dose of IP Is event serious?  Yes  No	Serious enter Serious Criteria code (see codes below)  Yes  No	Relationship Is there a reasonable possibility that the Event may have been caused by IP or an Amgen device used to administer the IP?		Outcome of Event -Resolved -Not resolved -Fatal -Unknown	Check only if event is related to study procedure eg, biopsy
	Day Month Year	Day Month Year			<Device> <Device> <Device> <Device> No/ Yes No/ Yes No/ Yes No/ Yes			
Serious Criteria: 01 Fatal 02 Immediately life-threatening 03 Required/prolonged hospitalization 04 Persistent or significant disability /incapacity 05 Congenital anomaly / birth defect 06 Other medically important serious event								
4. Was subject hospitalized or was a hospitalization prolonged due this event?  No  Yes If yes, please complete all of Section 4								
Date Admitted			Date Discharged					
Day Month Year			Day Month Year					
5. Was IP/drug under study administered/taken prior to this event?  No  Yes If yes, please complete all of Section 5								
IP/Amgen Device:  Oprozomib  blinded  open label  Oprozomib  blinded  open label	Date of Initial Dose	Date of Dose	Dose	Route	Frequency	Action Taken with Product 01 Still being Administered 02 Permanently discontinued 03 Withheld	Lot # and Serial #	
	Day Month Year	Day Month Year					Lot # _____  Unknown Serial # _____  Unavailable / Unknown	

Approved

Onyx Therapeutics  
 Oprozomib ER Tablets

Clinical Study Protocol No. OPZ007  
 Page 156 of 223

 Study # 20130411 Oprozomib	Electronic Serious Adverse Event Contingency Report Form For Restricted Use
--	---

Site Number		Subject ID Number													
6. CONCOMITANT MEDICATIONS (eg, chemotherapy) Any Medications?  No  Yes If yes, please complete:															
Medication Name(s)	Start Date			Stop Date			Co-suspect		Continuing		Dose	Route	Freq.	Treatment Med	
	Day	Month	Year	Day	Month	Year	No ✓	Yes ✓	No ✓	Yes ✓				No ✓	Yes ✓
7. RELEVANT MEDICAL HISTORY (include dates, allergies and any relevant prior therapy)															
8. RELEVANT LABORATORY VALUES (include baseline values) Any Relevant Laboratory values?  No  Yes If yes, please complete:															
Date	Test	Unit													
			Day	Month	Year										
9. OTHER RELEVANT TESTS (diagnostics and procedures) Any Other Relevant tests?  No  Yes If yes, please complete:															
Date	Additional Tests	Results	Units												
				Day	Month	Year									

Approved

Onyx Therapeutics  
 Oprozomib ER Tablets

Clinical Study Protocol No. OPZ007  
 Page 158 of 223

